
To assess durability of clinical outcomes after treatment with IMP from Baseline (i.e. first dose^b of IMP) to Study Visit 1 in study participants previously treated with IMP as part of the Phase III ORACLE MS and CLARITY/CLARITY-EXT clinical trials.
	
Tertiary endpoints to be evaluated via retrospective data collection from medical records or at Study Visit 1:
 
 • Proportion of study participants being bedridden^d • Time from first dose^b of IMP to first use of an ambulatory device^d • Time from first dose^b of IMP to first use of a wheelchair^d • Annualized Relapse Rate (ARR) from time of first dose^b of IMP to Study Visit 1, and by 2-year intervals • Time to conversion to Clinically Definite MS (CDMS) (For ORACLE MS study participants only)

Exploratory Objectives	Endpoints (Outcome Measures)
	
 • Proportion of study participants diagnosed as Secondary Progressive MS (SPMS) without relapses in the 3 months prior to SPMS diagnosis • Proportion of study participants diagnosed as SPMS with relapses in the 3 months prior to SPMS diagnosis • Proportion of study participants diagnosed as Primary Progressive MS (PPMS) (For ORACLE MS study participants only)

To assess impact on quality of life and cognitive outcomes after treatment with IMP during the period from the last clinical visit in the CLARITY/CLARITY-EXT/ORACLE MS clinical trials to Study Visit 1 in study participants previously treated with IMP as part of the Phase III ORACLE MS and CLARITY/CLARITY-EXT clinical trials.
	
Tertiary endpoints to be evaluated at Study Visit 1:
 
 • Change in EuroQoL-5 Dimension Questionnaire (3 level version) (EQ-5D-3L) • Change in cognition as measured by the following assessments (to be collected for ORACLE MS subjects only in countries where these instruments were used in the CLASSIC MS study): 
 ○ The Brief Visuospatial Memory Test – Revised (BVMT-R) ○ Symbol Digit Modality Test (SDMT)

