Time-to-event data will be calculated from first dose of IMP in the parent study and will be presented using Kaplan-Meier estimates or cumulative incidence curves as appropriate. The analytical approach will be further detailed in the SAP.

Genetic variations will be analyzed descriptively. In addition, association of genetic variations with patients experiencing long-term response will be analyzed.

Adverse events will be summarized by number and frequency of patients with events.

Endpoint	Statistical Analysis Methods
Primary	Percentage and 95% CI
Secondary	Percentage and 95% CI
Tertiary/Exploratory	Descriptive statistics and time-to-event analyses as described above

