6.5 Final Analysis

All analyses described in this IAP will be performed after the final database lock (see Section 14

for further details on analyses) and summarized in final study report. Results of the final analysis will be summarized in a formal study report.

7 Changes to the Planned Analyses in the Clinical Study Protocol

There are no changes to the analyses planned per protocol.

8 Analysis Populations and Subgroups

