14.3.2 Durability of clinical outcomes

Durability of clinical outcomes will be summarized descriptively and evaluated via retrospective data collection from medical records or at Study Visit 1:

- Proportion of study participants being bedridden
- Time from first dose of IMP to first use of an ambulatory device
- Time from last dose of IMP to first use of an ambulatory device
- Time from first dose of IMP to first use of a wheelchair
- Time from last dose of IMP to first use of a wheelchair
- Number of MS relapses between the end of parent study to Study Visit 1
- ARR from time of first dose of IMP to SV1, and by 2-year intervals
- ARR from time of last dose of IMP to SV1, and by 2-year intervals
- % and Time to conversion to CDMS (For Cohort D participants only)
- Proportion of study participants diagnosed as Secondary Progressive MS (SPMS) without relapses in the 3 months prior to SPMS diagnosis
- Proportion of study participants diagnosed as SPMS with relapses in the 3 months prior to SPMS diagnosis
- Proportion of study participants diagnosed as Primary Progressive MS (PPMS) (For Cohort D participants only)

Computational rule:

Participants being bedridden, first use of an ambulatory device and first use of a wheelchair are collected on “ambulatory - bedridden status and first use of wheelchair” eCRF page.

Participants diagnosed as SPMS with and without relapses in the 3 months prior to SPMS diagnosis are collected on “History of MS onset” eCRF page and Participants diagnosed as PPMS are collected on “conversion to CDMS” eCRF page.

Time to first ambulatory device/wheelchair

Kaplan Meier curve and estimates including number of subjects at risk, number of subjects with an event and subject censored will be presented for time to first ambulatory and wheelchair from first and last dose of IMP administered, by treatment group (exposed vs never exposed) and overall

Computation rule:

Whichever come first will be considered as an event:

- 1) CRF Ambulatory device page, wheelchair use date
- 2) CRF Ambulatory device page, ambulatory device use date
- 3) EDSS score ≥ 6
- 4) Death due to MS

Kaplan Meier SAS code:

AVAL = time-to-event response variable

CENSOR = censoring variable (0 = event, 1 = no event)

TRT= Trt group (“Exposed to Clad” “Never exposed to Clad”)

Code:

```
PROC LIFETEST DATA=ADTTE OUTSURV=RESULTS ALPHA=0.05 METHOD= KM Conftype =  
Loglog;  
TIME AVAL*CENSOR(1);  
STRATA TRT;  
RUN;
```

Annualized Relapse Rate:

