ARR from time of FDIMP to Study Visit 1 is calculated for each treatment group:

$$\text{ARR} = [(\text{sum of relapses} * 365.25) / (\text{sum of time on study in days until SV1})]$$

ARR from time of FDIMP to Study Visit 1 and by 2-year intervals is calculated for each treatment group:

$ARR = [(sum\ of\ relapses\ *365.25) / (sum\ of\ time\ on\ main\ study\ by\ 2\text{-}year\ intervals\ in\ days\ until\ SV1)]$

Time on study = Study Visit 1 – first dose of IMP +1

ARR from time of last dose of IMP to Study Visit 1 will be calculated similarly.

Table 5: Time window for ARR by 2-year intervals

Cumulative intervals	Time intervals
Less than 2 years	1 to 730 days
2 nd years to 4 th years	731 to 1461 days
4 th years to 6 th years	1462 to 2191 days
6 th years to 8 th years	2192 to 2922 days
X th years to Y th years...	Truncate (X*365.25 +1) to truncate (Y*365.25) days

Time to CDMS (Cohort D only)

Number of participants who converted to CDMS since first and last dose administered will be summarized descriptively.

Both information collected in “Conversion to CDMS” eCRF page and ORACLE MS parent study dataset will be used to identify participants who converted to CDMS after first/last dose of IMP.

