Table 15.2.4.4.1	MRI characteristics at Study Visit 2 of long-term responders vs non-responders – Cohort D- MRISS analysis set		
Table 15.2.4.4.2	MRI characteristics at Study Visit 2 of long-term responders vs non-responders – Cohort D – MRISS analysis set (Sensitivity Def B)		
Table 15.2.4.4.3	MRI characteristics at Study Visit 2 of long-term responders vs non-responders – Cohort D – MRISS analysis set (Sensitivity Def C)		

15.2.5: Tertiary Endpoint 1			
Table 15.2.5.1	Real-world treatment patterns in study participants – Cohort A- FAS analysis set		U
15.2.6: Tertiary Endpoint 2			
Table 15.2.6.1	Durability of clinical outcome– Cohort A – FAS analysis set		U
Table 15.2.6.2	Kaplan Meier- Time to first ambulatory device/wheelchair - Cohort A -FAS analysis set	Y	U
Figure 15.2.6.1	Kaplan Meier- Time to first ambulatory device/wheelchair by Exposed/Never Exposed Group - Cohort A -FAS analysis set	Y	U
Figure 15.2.6.2	Kaplan Meier - Time to First Ambulatory Device/Wheelchair - Cohort A - FAS Analysis Set	Y	
15.2.7: Tertiary Endpoint 3			
Table 15.2.7.1	Change in Quality of life outcomes – Cohort A- FAS analysis set	Y	U
Table 15.2.7.2	Change in Cognition outcomes (BVMT-R score)– Cohort D- FAS analysis set		U
Table 15.2.7.3	Change in Cognition outcomes (SDMT score) – Cohort D- FAS analysis set		U
15.2.8: Tertiary Endpoint 4			
Table 15.2.8.1	Change in MRI assessment from Baseline to Study Visit 2– Cohort A -MIRISS analysis set		U
15.2.9: Tertiary Endpoint 5			
Table 15.2.9.1	Responder rate by HDA/Non-HDA patients – Cohort B-FAS analysis set		U
15.2.10: Additional analysis			
Table 15.2.10.1	Additional analysis: Comparison between baseline characteristics from Non-CLASSIC/CLASSIC patients- WPS analysis set		U
15.2.11: PGX Analysis (tables will be repeated for each SNP or combination of SNPs.)			
Table 15.2.11.1.1	Proportion of patients using a wheelchair (EDSS>=7) the majority of the time in the 3 months prior to Study Visit 1 or bedridden – Cohort A – Subgroup with Presence of SNP1 gene - PGX Population		
Table 15.2.11.2.1	Proportion of patients with EDSS of 6.0 or higher since last dose of IMP – Cohort A – Subgroup with Presence of SNP1 gene - PGX Population		

Table 15.2.11.3.1	Clinical characteristics at Study Visit 1 of long-term responders vs Non-Responders – Cohort A– Subgroup with Presence of SNP1 gene - PGX Population		

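### Time to CDMS is a named endpoint with a time-to-event method in the protocol, but the SAP's only analysis rule for it is a count of converters, with no time estimate and no listed output

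*SAP*

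**What the plan says.** The endpoint tables of the protocol (Sections 1.1 and 3) and of the SAP (Section 5) all include time to CDMS conversion, restricted to ORACLE MS participants. The bullet list in SAP 14.3.2 repeats it, asking for the percentage "and Time to conversion to CDMS (For Cohort D participants only").

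On method, Protocol 9.4 says that time-to-event data are measured from the first dose in the parent study and "will be presented using Kaplan-Meier estimates or cumulative incidence curves as appropriate". It leaves further detail to the SAP.

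The SAP supplies that detail for one endpoint only. In 14.3.2, Kaplan-Meier curves and estimates "will be presented for time to first ambulatory and wheelchair from first and last dose of IMP administered", with an event rule and PROC LIFETEST code. For CDMS the same section says: "Number of participants who converted to CDMS since first and last dose administered will be summarized descriptively". It then names the two data sources that identify converters, the CLASSIC conversion page and the ORACLE MS dataset. It gives no estimator, denominator, censoring date or handling of death.

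The output list in Appendix 17.1 follows the same pattern. Its only Kaplan-Meier table (15.2.6.2) is titled "Kaplan Meier- Time to first ambulatory device/wheelchair - Cohort A -FAS analysis set", and the two Kaplan-Meier figures have the same scope. No output is named for CDMS, and the single durability table (15.2.6.1) is labelled Cohort A. SAP Section 7 states: "There are no changes to the analyses planned per protocol".

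**The concern.** A count of converters does not answer a time-to-event question. It gives no median, no curve and no conversion probability at a stated year. It also ignores how long each participant was observed. If the count is divided by all Cohort D participants, anyone whose information stops before conversion falls among the non-converters by arithmetic.

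Observation time can differ. Protocol 4.1 and 5.1 allow data from the records of deceased and lost-to-follow-up patients, and SAP 10.1 tabulates time since first dose in bands that start below 5 years. In the same section, the annualized relapse rate is divided by time on study; CDMS has no such adjustment.

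At stake is a named endpoint that the programmed outputs would not deliver, with a percentage in its place that cannot be read as conversion by any particular year.

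**Working it through.** **Step 1. Is there a figure in the plan to reproduce?** No. Neither document states an expected conversion rate or time, so the check compares the passages and then illustrates the size.

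**Step 2. Passages side by side.**

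| Item | Ambulatory device/wheelchair | CDMS |
|---|---|---|
| Named as time-to-event | Yes | Yes |
| Estimator in SAP 14.3.2 | Kaplan-Meier | None; count only |
| Event rule | Four sources, earliest counts | Two data sources; no criteria stated |
| Code | PROC LIFETEST | None |
| Output in 17.1 | One table, two figures | None named |

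The analysis is feasible. SAP 14.1 uses the CDMS conversion date, collected in the parent study or afterwards until Study Visit 1 (SV1), to compute disease duration for ORACLE MS patients.

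**Step 3. Who could have short follow-up?** SAP 6.2 puts the early termination of ORACLE MS, and the end of cladribine dosing, in October 2011. Protocol 4.1 starts enrolment in about Q3 2019. From October 2011 to 1 July 2019 is about 7.7 years, so an ORACLE MS participant who reaches SV1 is at least that far from last dose. Short follow-up is therefore mainly a matter of deceased or lost patients included from records. Their number is not given.

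**Step 4. Size under assumed inputs.** Let P be the true 10-year conversion probability and s the share of participants whose follow-up ends uniformly between 2 and 5 years, the rest being followed for 10 years. With exponential times, λ = −ln(1 − P)/10. Average conversion in the short-follow-up group is F = 1 − [e^(−2λ) − e^(−5λ)]/(3λ). The crude percentage is (1 − s)P + sF, so the shortfall is s(P − F).

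| P | λ | F | Shortfall, s = 5% | s = 30% | s = 40% |
|---|---|---|---|---|---|
| 30% | 0.0357 | 11.7% | 0.9 points | 5.5 | 7.3 |
| 50% | 0.0693 | 21.4% | 1.4 | 8.6 | 11.4 |
| 70% | 0.1204 | 34.0% | 1.8 | 10.8 | 14.4 |

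For P = 50% and s = 30%: 0.7 × 50% + 0.3 × 21.4% = 41.4%, against 50%.

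Simulation with 400,000 participants per scenario agrees with these crude percentages to within about 0.2 points. In it Kaplan-Meier recovers the true value (50.1% for this case), because the simulated censoring is unrelated to conversion. If conversions are front-loaded (Weibull, shape 0.6), the shortfall is smaller: with P = 50% and s = 30%, the crude value is 44.1%. Over all scenarios the shortfall is about 1 to 14 points.

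**Step 5. Would summarising time among converters repair it?** No. In the exponential case with a true median of 10 years and s = 30%, the median among converters alone is about 3.5 years.

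**The case against.** The best defence is that this is thin drafting and that the endpoint has not been replaced. The SAP bullet names time as well as percentage. SAP Section 4 bases the plan on protocol Section 9, and Section 7 withdraws nothing, so the protocol's method arguably still applies. SAP 9.5 has a partial-date rule for time-to-event analyses that is not limited to mobility. Table 15.2.6.1 covers Cohort A, which contains the ORACLE MS participants. The endpoint is tertiary, in an exploratory study with no hypothesis test.

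Much of this stands, and it limits what can be said. Four stronger readings are tempting but unsupported:

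- *The SAP has a rule that counts short follow-up as non-conversion.* It has none. It gives no denominator, and elsewhere it keeps unknowns apart: the primary model drops unknown outcomes, and responder status can be not determined. The understatement follows only if the count is divided by everyone.
- *The bias is a known figure.* A hazard of 0.08 per year with 25% of patients followed for only 4 years gives 0.75(1 − e^(−0.8)) + 0.25(1 − e^(−0.32)) = 48.1% against 55.1%, about 7 points. Neither input is in the documents.
- *Chart-only patients have short follow-up.* Protocol 4.1 collects chart data for all patients up to SV1, and Step 3 puts those reaching SV1 at about 7.7 years or more since last dose.
- *Results must be shown by randomised arm.* SAP 8.2.1 and Section 14 analyse as treated, exposed against never exposed.

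The defence does not remove the gap itself. Under the heading for this endpoint the only analysis rule is a count. The 9.5 rule handles dates that cannot be ordered against the start date; it sets no censoring date for unconverted participants. No listed output is named for the result.

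**Conclusion.** The point holds as a gap between the protocol and the SAP. The protocol specifies a time-to-event method, the SAP does not carry it through for CDMS, and Section 7 does not declare the difference. Followed as written, the SAP produces no time estimate. That conclusion needs no assumption about follow-up.

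The second part is conditional. A percentage over all Cohort D participants understates conversion in proportion to the share with incomplete follow-up, by about 1 to 14 points under the assumed inputs in Step 4. If only 5% have short follow-up, the shortfall is about 1 to 2 points in the exponential cases. Kaplan-Meier removes it only if the end of the record is unrelated to conversion, which is open to doubt with records-based follow-up.

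No primary or secondary result is affected. The change should be made, but it is of moderate importance at most.

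**What to change.** In SAP 14.3.2, specify for Cohort D:

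- **Estimator:** Kaplan-Meier, or cumulative incidence with death as a competing event, for time from first dose to CDMS, with estimates at fixed years.
- **Censoring:** unconverted participants at SV1, or at the last documented assessment if earlier, with a statement that this censoring is assumed non-informative.
- **Event definition:** ORACLE MS used the Poser criteria (SAP 6.2), while Protocol 8.1.1.8 uses McDonald 2017. State which counts as the event in each period; otherwise one curve joins two definitions.
- **Groups:** overall and by the SAP's exposure groups, with a caution. SAP 6.2 says that CDMS converters in the first 96 weeks stopped blinded drug and were offered interferon, whereas those meeting McDonald 2005 criteria at the end of that period were allocated open-label cladribine. SAP 8.2.1 then counts any cladribine dose as exposed. A placebo patient who converts early tends to stay never exposed, and one who does not may move to exposed, so the grouping partly depends on the outcome. A display by initial-period arm is an optional addition.
- **Since-last-dose version:** if it is kept, say how conversions before the last dose are handled.

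Add one Cohort D table and one figure to Appendix 17.1. The conversion dates are already collected and the PROC LIFETEST code can be adapted. The cost is a little extra programming, plus the work of settling the event definition.

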14.3.3 Quality of Life and cognitive outcomes

EQ-5D-3L:

The EQ-5D-3L consists of two components - the EQ-5D descriptive system and the EQ visual analogue scale (EQ VAS). The descriptive system comprises the following five dimensions:

- Mobility
- self-care
- usual activities
- pain/discomfort
- anxiety/depression

Each dimension has three levels: no problems, some problems, extreme problems (labelled 1–3). The respondent is asked to indicate his health state by checking the box against the most appropriate statement in each of the five dimensions. The EQ-5D descriptive system will be summarized for each dimension as continuous variable at study visit 1.

Respondents indicate their self-rated health on the EQ VAS, numbered from 0 to 100 where the endpoints are labelled “Best imaginable health state” (100) and “Worst imaginable health state” (0). This information can be used as a quantitative measure of health outcome as judged by the individual respondents and will be summarize descriptively at study visit 1.

EQ-5D descriptive system and EQ VAS change from the latest assessment prior to or on first dose of IMP will also be summarized descriptively. In case of missing date in parent study, visit labels (e.g., Screening Visit, Baseline Visit, Unscheduled Baseline Visit) will be used to determine baseline visit.

Computation rule:

If there is no EQ-5D score before or on the first dose of IMP day, then the change will not be calculated.

BVMT-R (Cohort D only):

BVMT-R performance test will be summarized using the following raw scores: “Total recall”, “Delay recall”, “Percent retained (%)” and “Learning Consistency (%)”.

Raw scores at study visit 1 and change from ORACLE MS study latest assessment prior to or on first dose of IMP will be summarized descriptively.

Computation rule:

If there is no BVMT-R score before or on the first dose of IMP day, then the change will not be calculated.

SDMT (Cohort D only):

Total SDMT score (i.e. oral score from sdmt eCRF page) at study visit 1 and change from latest assessment prior to or on first dose of IMP will be summarized descriptively.

Computation rule:

If there is no SDMT score before or on the first dose of IMP day, then the change will not be calculated.

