8.10 Health Economics

Not Applicable.

9 Statistical Considerations

One interim and 1 final analysis are planned for this study.

Study data will be integrated with study data from the parent studies as required to perform the statistical analyses.

Generally, data will be analyzed descriptively with the following measures: mean with standard deviation, median with interquartile range, minimum and maximum for continuous variables and counts with percentages for categorical variables. Missing data will also be summarized. Patients' demographic factors and clinical characteristics at enrolment will be summarized descriptively as detailed above.

As the study visits are around 10 years after the initial treatment with IMP in the parent studies, it is likely that only a specific type of participants from these trials is available for follow-up. A potential selection bias will be evaluated by comparing the characteristics of those patients randomized to the parent studies and those patients included in this study.

Methodological approaches which evaluate and address this potential selection bias will be further detailed in the Statistical Analysis Plan (SAP). Differences in study populations will be considered when making inferences based upon study results. With this in mind, analyses

will generally be exploratory and for hypothesis generating purposes. Parameter estimates with associated 95% confidence intervals (CIs) will be reported for the study endpoints, as appropriate

The analytical approach for all endpoints is described below and will be further detailed in the integrated Analysis Plan (iAP).

All procedures outlined within this section will be undertaken using a SAS statistical analysis software (version 9.4 or higher).

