9.4 Statistical Analyses

The primary endpoint of this study will be evaluated by determining the percentage and 95% CI of patients using a wheelchair the majority of the time in the 3 months prior to Study Visit 1 or patients bedridden any time prior to Visit 1 (as defined in Section 8.1.1.1) for each Cohort and the appropriate subgroups/subsets as defined above in Section 9.3. Forest plots will also be used to display these results.

In addition, proportions adjusted for participation in previous parent studies, as well as other patient characteristics which are deemed to be prognostic for the primary endpoint will be determined applying a logistic regression model. Variables with multiple levels of discrete values will be modeled as categorical variables, and variables with continuous scales (e.g. age) may be modeled as a continuous covariate or categorized where appropriate.

The secondary endpoint, the proportion of patients with EDSS of 6.0 or higher as determined by EDSS documentation or alternative clinical description in medical records after last IMP from parent study. will be presented together with the corresponding 95% CI for each Cohort and appropriate subgroups/subsets as defined above. The results of the confidence scale of EDSS values will be presented descriptively and may be used to interpret EDSS results.

The clinical and MRI characteristics of study participants will be evaluated descriptively by the subgroup long-term responders for Cohort A.

Tertiary endpoints collected retrospectively or at Study Visit 1 will be analyzed descriptively.

Analyses of the change in EQ-5D-3L and change in cognition from the last clinical visit in the parent studies to Study Visit 1 in study participants previously treated with IMP as part of the parent studies will also be performed according to instrument developer instructions and analyzed descriptively to assess the durability of treatment effect.

Similarly, changes in MRI assessment from the last clinical visit in the parent studies to Study Visit 2 will be analyzed descriptively.

In addition, responder rates in high-disease activity (HDA) patients versus the responder rate in non-HDA patients from the CLARITY/CLARITY-EXT population will be analyzed descriptively.

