9.5 Handling of missing data/ Presentation of continuous and qualitative variables

It is anticipated that missing/not reported data will feature many of the endpoints, especially BVMT-R and SDMT (see section 14.3.3). No imputation will be done for these assessments.

In general, missing or partial dates will be imputed as follows:

- If year and month available but day is missing, impute day to 15
- If only year available, impute day and month to 15JUN
- If date is completely missing, then no imputation will be done, except for Concomitant Medication end dates: if end date is completely missing (day, month and year) and partial or complete start date then end date will be imputed to be the last study assessment date.

In addition, for concomitant medication dates:

- If imputed start date is after end date, then the start date will be set equal to end date.
- If imputed end date is before start date, then the end date will be set equal to start date.

For time to event analyses, if partial date does not determine whether event occurred before or after start date, then analysis date will be set equal to start date, subject will be censored and time to censoring = 1/365.25.

Continuous variables:

Continuous variables will be summarized using descriptive statistics, i.e.

- number of subjects (N),
- number of subjects with non-missing values,
- number of subjects with missing values
- mean and standard deviation,

- median, 25th Percentile - 75th Percentile (Q1-Q3),
- minimum, and maximum.

Qualitative variables:

Qualitative variables will be summarized by counts and percentages.

There are no plans for any formal statistical inference. This study will adhere to the Guidelines for Good Pharmacoepidemiology Practices (GPP). Data evaluation and interpretation will be based on point estimates and 95% corresponding confidence intervals (CI). Due to the exploratory nature of the study, an adjustment for multiple comparisons is not required.

Analyses will be performed using SAS® Software version 9.4 or higher.

10 Study Participants

The subsections in this section describe the specifications for reporting participant disposition and study discontinuations.

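### SAP 14.3.3 summarises the three-level EQ-5D-3L items as continuous, against SAP 9.5, and does not say how change in them will be shown

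*SAP*

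**What the plan says.** SAP 14.3.3 describes the five EQ-5D dimensions and their scale: "Each dimension has three levels: no problems, some problems, extreme problems", labelled 1 to 3. It then says: "The EQ-5D descriptive system will be summarized for each dimension as continuous variable at study visit 1". A separate sentence covers change: "EQ-5D descriptive system and EQ VAS change from the latest assessment prior to or on first dose of IMP will also be summarized descriptively". A computation rule adds that the change is not calculated when there is no score on or before the first dose.

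The rules for presenting data are elsewhere. SAP 9.5 says: "Qualitative variables will be summarized by counts and percentages". For continuous variables it lists N, non-missing and missing counts, mean, SD, median, quartiles, minimum and maximum. The opening text of Protocol section 9 sets the same division, introduced by the word *generally*, with "counts with percentages for categorical variables".

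SAP section 7 declares no changes to the analyses planned in the protocol. The output list in SAP 17.1 has one quality-of-life table, 15.2.7.1, for Cohort A, and it is also marked for the interim analysis. No shift table and no EQ-5D index score is named.

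**The concern.** An item answered by ticking one of three boxes is ordinal. A mean of codes 1 to 3 treats the step from no to some problems as equal to the step from some to extreme problems. It also does not directly give what a reader wants from the item, namely the share of patients with any problem or an extreme problem in mobility, self-care and so on.

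The SAP's own practice points the other way. It summarises worst EDSS, another ordinal scale, by category (14.2.1), and within 14.3.3 it describes only the 0 to 100 EQ VAS as a quantitative measure. Since no index score is planned, the five items and the VAS make up the whole EQ-5D output, and no other listed table would supply the level distribution.

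The protocol endpoint is change in EQ-5D-3L, so the display of change matters more than the display at one visit. Improvement in some patients can offset worsening in others, and the SAP does not say whether its display of change will separate them.

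**Working it through.** The documents give no figure to reproduce. The check is whether the continuous statistics in SAP 9.5 would let a reader recover the categorical result. All distributions below are assumed, with 100 patients.

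**Level at Study Visit 1 (three possible values)**

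The mean alone is ambiguous:

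| Counts at levels 1, 2, 3 | Mean | SD |
|---|---|---|
| 0, 100, 0 | 2.0 | 0 |
| 20, 60, 20 | 2.0 | 0.636 |
| 50, 0, 50 | 2.0 | 1.005 |

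SAP 9.5 also reports n and SD. With mean m and SD s, put S1 = n·m and S2 = (n − 1)·s² + n·m². Three equations then determine the three counts:

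- n1 + n2 + n3 = n
- n1 + 2·n2 + 3·n3 = S1
- n1 + 4·n2 + 9·n3 = S2

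Hence n3 = (S2 − 3·S1 + 2n)/2, n2 = S1 − n − 2·n3, and n1 is the remainder.

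For the second row, S1 = 200 and S2 = 99 × 0.636² + 400 = 440 (rounded). So n3 = (440 − 600 + 200)/2 = 20, n2 = 200 − 100 − 40 = 60 and n1 = 20, which are the counts we started from.

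With mean and SD rounded to two decimals, the largest error over 5,000 simulated distributions at each size was 0.96 percentage points (n = 100), 1.38 (n = 400) and 1.29 (n = 587, the 30% recruitment row in Protocol 9.2). The level shares are therefore unreadable in the planned table, but not lost.

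**Change (five possible values, −2 to +2; positive is worse)**

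Now n, mean and SD give three equations for five unknown counts. Median, quartiles and range only narrow the possibilities.

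| | Counts at −2, −1, 0, +1, +2 | |
|---|---|---|
| | 6, 0, 88, 0, 6 | 1, 20, 58, 20, 1 |
| Sum | −12 + 12 = 0 | −2 − 20 + 20 + 2 = 0 |
| Sum of squares | 24 + 24 = 48 | 4 + 20 + 20 + 4 = 48 |
| Mean | 0.00 | 0.00 |
| SD = √(48/99) | 0.696 | 0.696 |
| Median; Q1 to Q3 | 0; 0 to 0 | 0; 0 to 0 |
| Minimum; maximum | −2; 2 | −2; 2 |
| Improved / worsened | 6% / 6% | 21% / 21% |

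Every continuous statistic in SAP 9.5 agrees, while the shares improved and worsened differ by 15 percentage points each. If no patient moved by two levels, change would take at most three values and the algebra above would again recover the counts.

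**Reference visit**

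Protocol 9.4 measures EQ-5D-3L change from the last clinical visit in the parent study, and the objectives table in SAP section 5 repeats this. SAP 14.3.3 measures it from the latest assessment before or on the first dose of IMP. A shift table cannot be built until one of these is chosen.

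**The case against.** The best case for leaving the text alone has five parts.

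- **The continuous sentence covers one visit only.** It concerns the level at Study Visit 1, where nobody is classed as improved or worsened. The sentence on change names neither type of summary, and the table shells are not in the documents. This stands. The words *score* and *calculated* suggest a numeric difference, but do not state one.
- **The summary is more than a mean.** A reader might infer that a mean change of +0.2 could equally be 20% worse by one level, 10% worse by two levels, or 40% worse and 20% better by one level. With 100 patients these have SDs of 0.40, 0.60 and 0.75 and ranges of 0 to 1, 0 to 2 and −1 to 1, so the SAP 9.5 statistics separate them. A reader might also infer that the plan cannot show what share have problems at Study Visit 1; the back-calculation shows that it can, awkwardly.
- **The protocol rule is general and does not classify the EQ-5D items.** True, but SAP 9.5 carries no such qualifier, and three labelled levels are qualitative on any ordinary reading.
- **Protocol 9.4 has an instrument-specific rule.** It says the analyses "will also be performed according to instrument developer instructions". Those instructions are not in the documents, so they support neither side and nothing here rests on them.
- **Disability is covered elsewhere.** The primary endpoint, EDSS of 6.0 or higher and bedridden status are reported as proportions, and ambulatory device or wheelchair use by Kaplan-Meier. This stands and limits the importance of the point. It does not supply the self-care, usual activities, pain/discomfort or anxiety/depression distributions.

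**Conclusion.** The point holds in limited form. Summarising the three-level items as continuous at Study Visit 1 conflicts with SAP 9.5, departs from the protocol's general rule, and is not declared in SAP section 7. At that visit the effect is poor presentation rather than lost information.

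For change, the defect is that the summary type is not specified. Information would be lost only if change is handled as continuous and some patients move by two levels; both are assumptions. The 6% against 21% contrast was constructed to show that the loss is possible and is not a forecast of its size. The documents do not support saying that the plan, as written, hides who improved or worsened.

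The consequence is confined to a tertiary, descriptive endpoint with no hypothesis test. It does reach published results, since EQ-5D-3L is also part of the interim output. The primary and secondary analyses are unaffected.

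**What to change.** Amend SAP 14.3.3 and the shell of Table 15.2.7.1 as follows:

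1. For each of the five dimensions, report n (%) at each level at the reference visit and at Study Visit 1, with the number missing.
2. For patients with both assessments, give a shift table, or n (%) improved, unchanged and worsened.
3. Keep continuous statistics, including change, for the EQ VAS.
4. State the reference visit once and reconcile Protocol 9.4 and SAP section 5 with SAP 14.3.3. If the pre-dose assessment is kept, list this under SAP section 7.

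The cost is a few sentences and a revised table shell. The level and change counts come from item responses already collected, so no new data are needed. SAP 6.4 says the interim results have already been disseminated, so the change would apply to the final analysis.
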